10.8.2 Vital Signs

Vital signs will be summarized using descriptive statistics.

10.8.3 Concomitant Medications

Concomitant medications, as well as rescue medications, will be summarized using descriptive statistics.

10.8.4 Other Observations Related to Safety

Physical, neurological, and nasal examination results, as well as other observations related to safety will be summarized in data listings.

10.9 Termination Criteria

Based on studies conducted with nasal CO₂ to date, it is not expected that serious safety issues will arise that would require the sponsor to discontinue parts or all of the study. If such issues do arise, the sponsor will, in consultation with Capnia, appropriate regulatory authority, and IRB take the steps necessary to discontinue the study.

There will be an ongoing analysis of the data, and as such there is the possibility of terminating the study early due to efficacy or lack of efficacy.

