5.4 Discontinuation

Based on trials conducted with nasal CO₂ to date, it is not expected that serious safety issues will arise that would require a discontinuation of the study. If such issues do arise, the sponsor, [name], will, in consultation with the Capnia, appropriate regulatory authority(ies), and/or IRB, take the steps necessary to modify or discontinue the trial.

Since this is an open-label, pilot study, there will be an ongoing review of the data. The trial may also be discontinued or modified in the event that the study treatment is not showing any signs of efficacy.

The criteria for the discontinuation of the participation of individual subjects are explained in Section 6.3.

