10.0 STATISTICAL METHODS AND ANALYSIS

10.1 General Considerations

Tests will be conducted with a two-sided alpha = 0.05. Descriptive statistics and 95% confidence intervals will be presented with all analyses.

One interim analyses will be performed after 12 subjects have completed the study. All efficacy and safety analyses will be performed at the conclusion of the study.

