10.3.2 Method and Timing of Assessing Efficacy

Since this is an open-label, pilot study, all efficacy analyses will be performed after 12 subjects have treated at least 1 cluster attack.

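### Sections 10.1 and 10.3.2 disagree on when efficacy is analysed, and 10.9 permits an early stop for efficacy with no stated looks or boundary

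*Combined protocol and SAP*

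**What the plan says.** Four sections bear on when the data are analysed and when the trial may end.

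- **10.1 General Considerations:** "One interim analyses will be performed after 12 subjects have completed the study". The next sentence reads "All efficacy and safety analyses will be performed at the conclusion of the study". The same section sets the test level, "Tests will be conducted with a two-sided alpha = 0.05", and promises 95% confidence intervals with all analyses. It attaches no stopping decision to the interim.
- **10.3.2 Method and Timing of Assessing Efficacy:** because the study is an open-label pilot, "all efficacy analyses will be performed after 12 subjects have treated at least 1 cluster attack".
- **10.9 Termination Criteria:** "There will be an ongoing analysis of the data", and therefore "there is the possibility of terminating the study early due to efficacy or lack of efficacy".
- **5.4 Discontinuation:** "there will be an ongoing review of the data", and "The trial may also be discontinued or modified in the event that the study treatment is not showing any signs of efficacy".

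No section gives the number or timing of looks under 10.9, a stopping boundary, a lack-of-efficacy criterion or an adjusted final test level. The planned size is 25 subjects in one arm. The synopsis names repeated measures ANOVA and t-tests for within-group change.

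**The concern.** There are two linked problems.

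The first is the schedule. 10.1 and 10.3.2 both use the number 12 but count different things: subjects who have completed, and subjects who have treated one attack. Each section also assigns the whole of the efficacy analysis to a different time. A team following the plan cannot tell which event triggers the analysis, or whether that analysis is a look on the way or the main result.

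The second is the efficacy stop. In an open-label study the results can be seen as they accrue. A trial that may end whenever they look good tends to end when chance has helped, so the estimate from a stopped trial is too high on average, and the planned 95% interval does not allow for that. The effect estimate is a main product of a pilot and is likely to inform whether and how a later trial is designed.

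**Working it through.** **1. Timing passages compared**

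| | 10.1 | 10.3.2 |
|---|---|---|
| Event counted to 12 | Study completed | At least one attack treated |
| When all efficacy analyses occur | Study conclusion | After that 12-subject event |
| Called an interim? | Yes | No |

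The two events can be far apart. A subject may treat an attack on the day of screening, yet complete as late as 84 + 7 = 91 days after it (5.3). Reading 10.3.2 as a description of the 10.1 interim leaves the events different and still contradicts 10.1 on when all efficacy analyses occur. Reading it as a minimum before any efficacy analysis is possible, but the text does not say so. For the first-attack analysis both events can give the same 12 observations; the all-headaches analysis in 10.5 can differ.

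**2. Inputs for the size of the efficacy-stop problem**

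- From the plan: 25 subjects, a 12-subject point, two-sided 0.05.
- Assumed, because 10.9 gives no rule: the trial stops at a look if p<0.05 in the favourable direction in a one-sample t-test of the change (improvement positive); data are normal; the true effect is 0.3 or 0.5 SD.

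The plan gives no effect size, SD or power, so its sample size of 25 cannot be reproduced.

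**3. Smallest significant effect, in observed SD** (critical t divided by √n)

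- n = 12: 2.201/√12 = 0.635
- n = 25: 2.064/√25 = 0.413

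**4. Simulated early stops**

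Effects are in true SD unless marked.

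| Assumed looks | True effect | Stop early | Mean estimate if stopped | Mean over all trials |
|---|---|---|---|---|
| One, at 12 | 0.3 | 16% | 0.70 (0.85 in observed SD) | 0.33 |
| One, at 12 | 0.5 | 35% | 0.78 (0.90 in observed SD) | 0.55 |
| After every subject, 12 to 24 | 0.3 | 41% | 0.59 | 0.35 |
| After every subject, 12 to 24 | 0.5 | 75% | 0.66 | 0.56 |

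The all-trials bias is therefore 0.33 − 0.30 = 0.03 up to 0.56 − 0.50 = 0.06.

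The 0.635 threshold is a floor in observed SD only. In true-SD units, 36% (true effect 0.3) and 23% (true effect 0.5) of the favourable stops at 12 have a mean below 0.635. It is not a floor in points either: five changes of 1 and seven of 0 give a mean of 5/12 = 0.42 points with p = 0.017, which would stop the trial.

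**5. False-positive rate, under a zero-mean null only**

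For looks at 12 and 25 the test statistics have correlation √(12/25) = 0.693. From the bivariate normal distribution:

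- 0.05 at both looks: 0.084 overall, against 0.05 for a single look.
- 0.001 at 12 and 0.0497 at 25: 0.04995 overall.

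The primary endpoint is the greatest change within 30 minutes, whose mean need not be zero without a drug effect. In an illustration taking the best of three zero-mean changes, one final test already rejects in 48% of trials (correlation 0.8) or 90% (correlation 0.5). An extra unadjusted look at 12 raises this only to 52% or 91%.

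**The case against.** The strongest reply is that this is an open-label, single-arm pilot with no power calculation and no success criterion. 10.1 attaches no stopping decision to its interim, the p<0.05 stopping rule is an assumption made here, and the bias averaged over all trials is small. All of that is true, and it limits the weight of the point. It does not remove it: 10.9 does allow an efficacy stop, and a reader of a stopped trial sees the stopped estimate, not the average over trials that might have been.

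Several stronger readings are tempting, but the documents do not support them.

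- *That the plan breaks a promised overall error rate.* 10.1 sets a level for its tests and claims no overall level. The figure of 0.084 also needs a zero-mean null, which may not hold for a greatest change.
- *That any stopped trial must report at least 0.635 SD whatever the truth.* This holds only in observed-SD units.
- *That 5.4 contradicts 10.9.* 5.4 names only lack of efficacy. That is an omission and does not forbid an efficacy stop.
- *That the 12-subject triggers are faulty because neither requires a post-treatment evaluation.* A trigger sets timing; 10.4.2 sets who is analysed.

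**Conclusion.** The point stands as one that should be fixed. The conflict between 10.1 and 10.3.2 is plain on the page and nothing elsewhere resolves it. The efficacy stop in 10.9 is likewise plainly undefined. Confidence in both textual findings is high.

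The size is less certain because it rests on an assumed stopping rule, assumed look schedules, normal data and assumed true effects. On those assumptions a stopped trial reports, on average, roughly 1.3 times (0.66 against 0.5, looks after every subject) to 2.3 times (0.70 against 0.3, one look at 12) the true effect. The damage is to the reading of the pilot estimate and its interval, not to a confirmatory claim, since the plan makes none. What null value suits a greatest-change endpoint is a separate question that no stopping boundary would settle.

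**What to change.** 1. **10.1 and 10.3.2.** State one 12-subject milestone, chosen by the sponsor, in both places. Call that analysis the interim, and put the final efficacy and safety analyses at study conclusion. If the interim is to include the safety examinations, note that the physical, neurological and nasal examinations and vital signs are scheduled for repeat only at the End of Study Visit (8.1.3 to 8.1.5 and 8.2). The completed-study milestone is the one that captures them.
2. **10.9.** Replace the last sentence with wording such as: *Data will be reviewed as they accrue. The study may be ended early for lack of efficacy; it will not be ended early for efficacy.* The lack-of-efficacy review in 5.4 can stay as it is, because stopping for lack of efficacy does not cause the upward bias described here.
3. **If the sponsor wants to keep an efficacy stop,** pre-specify the looks and the boundary. One example is p<0.001 at 12 and p<0.0497 at 25, with no other efficacy looks; this totals about 0.05 under a zero-mean null only. Report any early-stop estimate as likely too high.

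The cost is wording in three sections, with no added subjects, visits or data. The downside is that the sponsor gives up unrestricted early stopping for efficacy.

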10.10 Accountability Procedure

For primary efficacy analyses, no adjustment for missing values will be made. Exploratory analyses may be performed using the last value carried forward (LVCF) method.

10.11 Deviation Reporting

Any significant deviations to the statistical analysis plan (Sections 10.1 through 10.11) will be addressed in the final report for this study.

11.0 DIRECT ACCESS TO SOURCE DATA/DOCUMENTATION

During the trial, Clinvest will conduct remote monitoring and safety oversight periodically. The clinical monitors may review eCRFs, at intervals throughout the study to verify appropriate inclusion of subjects, adherence to the protocol, and completeness, correctness, and accuracy of eCRF entries. Any source upload should be reviewed for privacy elements and removed. Source uploads should only include the subject enrollment number as identifying information.

The Investigator and Institution will permit authorized representatives of Capnia, its designees, the national health authorities, local authorities, and IRB direct access to source data/documents to conduct study-related monitoring, audits, IRB review, and regulatory inspections.

12.0 QUALITY CONTROL AND QUALITY ASSURANCE

It is Clinvest's responsibility for implementing and maintaining quality control and assurance with written SOPs to ensure the trial is conducted in compliance with GCP standards and all applicable federal, state, and local laws, rules, and regulations. Appropriate tools will be implemented by the site to facilitate quality management of the subject and continuity through the trial.

Quality control should be applied by all parties and to each stage of subject management, investigational product management and data handling to ensure all data are reliable and have been processed correctly. All clinical data are to be generated and processed by personnel with relevant clinical and GCP knowledge. Subject generated data should be preceded with appropriate subject training and technical support for questions that arise during the trial.

Agreements, made by Clinvest, the investigator, and Capnia, Inc. and/or with any other parties involved with clinical trial should be in writing in a separate agreement.

Capnia, Inc. has provided Clinvest a Letter of Authorization so that Clinvest may cross-reference, Capnia INDs #74,680 and 126,801. As the investigator-sponsor of this study, the ultimate responsibility for the quality and integrity of the trial data also resides with Clinvest. The investigator agrees to be responsible for the integrity of all study conduct at their site.

The study will be registered on ClinicalTrials.gov by Clinvest.

13.0 ETHICAL CONSIDERATIONS

This study will be conducted according to the applicable regulations and international standards of GCP.

All subjects for this study will be provided an informed consent form describing this study and providing sufficient information for subjects to make an informed decision about their

participation in this study. This consent form will be submitted with the protocol for review and approval by the appropriate IRB. The formal consent of a subject, using the IRB-approved informed consent form, will be obtained before that subject undergoes any study-specific procedure. This informed consent form must be signed by the subject or legally acceptable surrogate, and the Investigator-designated research professional obtaining the informed consent.

14.0 DATA HANDLING AND RECORD KEEPING

Data for this trial will be primarily collected in a web-based electronic data capture (EDC) REDCap platform. The EDC access will be supplied by Clinvest with relevant training support to sites. The site will be responsible for training study subjects in the EDC system. All data specified should be captured by the site personnel or subjects in the EDC system. All eCRFs are to be completely filled out by personnel administering the study procedures at the time of the visit. The eCRF will be considered the source document for all data collected other than laboratory and procedure findings, which will be uploaded into the eCRF as source. All data must be reviewed and signed by the investigator or sub-investigator at the conclusion of the study for each subject. The eCRFs should not be made available in any form to third parties, without written permission from the sponsor.

It is the investigator's responsibility for the collection and reporting of all clinical, safety, and laboratory data entered on the eCRF and confirmation the data is accurate, authentic, attributable, complete, and consistent. The investigator or sub-investigator must sign the eCRFs within the EDC system to attest the information contained with the eCRF is true and causality of any safety information has been assessed.

Study documentation includes all workbooks, worksheets, forms, lab reports, logs, signature pages, appointment schedules, investigator correspondence, electronic data (i.e. data stored on cds, flash drives, etc.), and regulatory documents. The original recording of an observation should be retained as the source document.

1. Investigator will maintain essential documents for the conduct of a clinical study and any other documentation as specified by applicable regulatory requirements.
2. Investigator will maintain a binder containing written informed consent records.
3. Conduct of study visits will be maintained on appropriate Source Documentation/Case Report Forms. Subject anonymity will be maintained on these forms by identification codes (i.e., subject initials and number). The Investigator's electronic signature will verify that all data entries in the CRF's are complete and accurate.

Protocol 15-001CA
Nasal CO₂

4. Investigator will maintain a Subject Identification Log. Information such as full name of subject, address, contact information, and additional subject identifiers will be recorded. This log will be kept confidential and not copied.
5. Investigator will maintain a Subject Screening/Enrollment Record. This record will record chronologically subjects who were seen for Screening/Enrollment, additional visits conducted to replace Nasal CO₂ dispensers, and completion/discontinuation information.
6. Clinvest will maintain an Investigational Product Assignment Log. This log will record chronologically study medication received from Capnia, Inc. as well as medication returned or destroyed at the completion of the study.

Government agency regulation and directives require all study documentation pertaining to the conduct of a clinical trial must be retained by the investigator for at least 2 years after the last approval of a marketing application in an International Conference on Harmonization (ICH) region or at least 2 years have elapsed since the formal discontinuation of clinical development of the investigational product. The investigator will maintain all study documentation on file in a secure and safe location. Clinvest will notify the investigator in writing when retention is no longer necessary. No study records will be destroyed without prior agreement between Capnia, Inc. and Clinvest.

